6.2. Analysis Visit Windows

Table 12. Analysis Visit Windows for Assessments

- Hematology, Serum Chemistry, Haptoglobin, and Central Laboratory for Globin and VCN

Timepoint	Month	Target Day	Analysis Visit Window (Study Day)	
			Start	End
Follow-up Post-drug product Infusion	M1	D30	1	45
	M2	D60	46	75
	M3	D90	76	113
	M4.5	D135	114	158
	M6	D180	159	225
	M9	D270	226	315
	M12	D360	316	405
	M15	D450	406	495
	M18	D540	496	585
	M21	D630	586	675
	M24	D720	676	*

* Last visit day on the study, if it is > 676

- Chronic Pain Assessment, Performance Status, Tanner Staging (for Subjects <18 years of age), and Central Laboratory for ISA

Timepoint	Month	Target Day	Analysis Visit Window (Study Day)	
			Start	End
Follow-up Post-drug product Infusion	M6	D180	1	270
	M12	D360	271	450
	M18	D540	451	630
	M24	D720	631	*

* Last visit day on the study, if it is > 631

- Cerebral MRA/MRI (and TCD if \leq 16 years of age), PFT, 6MWT, Local Laboratory for Hormonal Testing, Urinalysis, Coagulation analysis, Brain Natriuretic Peptide, Erythropoietin, Karyotyping and NGS as applicable

Timepoint	Month	Target Day	Analysis Visit Window (Study Day)	
			Start	End
Follow-up Post-drug product Infusion	M12	D360	1	540
	M24	D720	541	*

* Last visit day on the study, if it is > 541

- Iron Metabolism Studies

Timepoint	Month	Target Day	Analysis Visit Window (Study Day)	
			Start	End
Follow-up Post-drug product Infusion	M3	D90	1	180
	M9	D270	181	315
	M12	D360	316	450
	M18	D540	451	630
	M24	D720	631	*

* Last visit day on the study, if it is > 631

- Immunological Studies

Timepoint	Month	Target Day	Analysis Visit Window (Study Day)	
			Start	End
Follow-up Post-drug product Infusion	M3	D90	1	135
	M6	D180	136	225
	M9	D270	226	315
	M12	D360	316	540
	M24	D720	541	*

* Last visit day on the study, if it is > 541

- Exploratory PD analysis: ex vivo sickling

Timepoint	Month	Target Day	Analysis Visit Window (Study Day)	
			Start	End
Follow-up Post-drug product Infusion	M6	D180	1	225
	M9	D270	226	315
	M12	D360	316	405
	M15	D450	406	495
	M18	D540	496	585
	M21	D630	586	675
	M24	D720	676	*

* Last visit day on the study, if it is > 676

- Other exploratory PD analysis

Timepoint	Month	Target Day	Analysis Visit Window (Study Day)	
			Start	End
Follow-up Post-drug product Infusion	M3	D90	1	113
	M4.5	D135	114	158
	M6	D180	159	225
	M9	D270	226	315
	M12	D360	316	405
	M15	D450	406	495
	M18	D540	496	585
	M21	D630	586	675
	M24	D720	676	*

- **Hematology: RDW**

Timepoint	Month	Target Day	Analysis Visit Window (Study Day)	
Follow-up Post-drug product Infusion	M24	D720	Start	End
			1	*

* Last visit day on the study, if it is > 1

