3.11. Analysis Visit Windows

All evaluation visits are expected to occur following scheduled evaluation per the protocol. The data used in summaries will be tabulated per the evaluation visit as recorded on the CRF. If the evaluation visit is missing due to early withdrawal or missing visits but there is data from unscheduled or additional visit that is inside an analysis visit window as defined in [Appendix 6.2, Table 12](#), then the data from the unscheduled or additional visit will be used for the analysis visit window in data summaries.

For endpoints that are not Hb fractions, if subjects have multiple unscheduled or additional evaluations within an analysis visit window, the evaluation closest to the target visit date will be used in the summary tabulations. In case of evaluations equidistant to the target visit date within an analysis visit window, results of the earlier evaluation will be used. This applies to all assessments without designated visits.

For Hb fractions, if subjects have multiple unscheduled or additional evaluations within an analysis visit window, the mean of these evaluations will be used in the summary tabulations and the detailed rules can be found in [Section 4.4](#).

Windows for time course distributions of AEs and concomitant medications are based on the following time periods:

- ICF until prior to either initiation of mobilization or bone marrow harvest (ICF to < MB)
- Initiation of mobilization (or bone marrow harvest) until prior to initiation of conditioning (MB to < C)
- Initiation of conditioning until prior to initiation of neutrophil engraftment (NE) (C to < NE)
- Initiation of NE through Month 24 (NE to M24)
- Day 1 (drug product infusion) until prior to initiation of NE (D1 to <NE)
- Day 1 (drug product infusion) through Month 24 (D1 to M24)
- Informed Consent Form through Month 24 (ICF to M24)

Note: initiation of NE is counted as the first date of the 3 consecutive ANC assessments that are $\geq 0.5 \times 10^9/L$ obtained on different days after the initial post-transplant nadir by Day 43.

Windows for time course distributions of clinical laboratory shift tables (shift categories defined by CTCAE grade, Version 4.03) are based on the following time periods:

- Initiation of mobilization (or bone marrow harvest) until prior to initiation of conditioning (MB to < C)
- Initiation of conditioning until prior to initiation of NE (C to < NE)
- Initiation of NE through Month 12 (i.e., Day 365) (NE to M12)

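### Two SAP Table 12 windows open at Day 1, so a lone early unscheduled value can be tabulated as Month 12 (annual tests) or Month 24 (RDW)

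*SAP*

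**What the plan says.** SAP 3.11 sets the order of precedence.

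- Default: "The data used in summaries will be tabulated per the evaluation visit as recorded on the CRF".
- Exception: "If the evaluation visit is missing due to early withdrawal or missing visits but there is data from unscheduled or additional visit" and that value lies inside a Table 12 window, "then the data from the unscheduled or additional visit will be used for the analysis visit window in data summaries".
- Several candidates (endpoints other than Hb fractions): "the evaluation closest to the target visit date will be used in the summary tabulations".

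No earliest day and no maximum distance from target is given.

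In SAP 6.2, Table 12, every block's first window starts at Day 1. Two blocks matter here:

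- The block that covers cerebral MRA/MRI, TCD, "PFT, 6MWT, Local Laboratory for Hormonal Testing, Urinalysis, Coagulation analysis, Brain Natriuretic Peptide, Erythropoietin, Karyotyping and NGS as applicable". Its first window is Month 12: target Day 360, Day 1 to Day 540. Month 24 follows from Day 541.
- RDW. Its only window is Month 24: target Day 720, start Day 1, with the end footnoted "Last visit day on the study, if it is > 1". SAP 5.2 records this window as new in the current SAP version and gives no reason for the Day 1 start.

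Protocol Table 4 allows ±30 days at both Month 12 and Month 24. Protocol 4.5 and SAP 3.9 ask subjects who withdraw after infusion to complete the Month 24 assessments as an Early Termination visit. Protocol 6.1 and 6.2.32 allow scheduled procedures to be done at unscheduled visits.

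**The concern.** The substitution in SAP 3.11 is mandatory once its conditions are met, and the window is the only check on how old the substituted value may be. Where the first target is Day 30, a Day 1 start does little harm. Where it is Day 360 or Day 720, a value from the transplant period, or from a withdrawal in the first months, can be reported as a one-year or two-year result.

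The subjects affected would be those who missed the visit or left, so any substitution is selective. The early period also includes busulfan toxicity and transfused blood, so an early value may differ systematically from a later one.

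The results at stake are by-visit summaries:

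- secondary endpoints: PFT, 6MWT and erythropoietin;
- exploratory endpoints: cerebral MRA/MRI, TCD and BNP;
- by-visit laboratory tables: hormones, coagulation and RDW.

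The PFT shift table (SAP 4.4.3.4) and the MRI shift table (SAP 4.4.4) are included.

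**Working it through.** **1. Reproduce the table's own logic.** The internal cut-points in Table 12 are midpoints between neighbouring target days.

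- Annual block: (360 + 720)/2 = 540, which gives the 540/541 cut.
- Hematology, Month 21 to Month 24: (630 + 720)/2 = 675, which gives a Month 24 start of Day 676.

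Only the first lower bound in each block has no earlier neighbour, and it defaults to Day 1.

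**2. Reach of the two windows.**

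| Window | Target | Start | Early reach | Late reach | Protocol window | Early reach / protocol |
|---|---|---|---|---|---|---|
| Annual tests, Month 12 | 360 | 1 | 360 − 1 = 359 days | 540 − 360 = 180 days | ±30 days | 359/30 ≈ 12 |
| RDW, Month 24 | 720 | 1 | 720 − 1 = 719 days | open | ±30 days | 719/30 ≈ 24 |

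**3. Apply SAP 3.11 to example days.** Assume that the scheduled visit is missing and that the value shown is the only unscheduled or additional one.

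| Study day | Annual block label | Days before 360 | RDW label | Days before 720 |
|---|---|---|---|---|
| 10 | Month 12 | 350 | Month 24 | 710 |
| 43 | Month 12 | 317 | Month 24 | 677 |
| 100 | Month 12 | 260 | Month 24 | 620 |
| 541 | Month 24 | not applicable | Month 24 | 179 |

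The closest-to-target rule does not help in these cases, because there is nothing closer to choose.

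**4. Internal comparison for RDW.** SAP Table 7 lists RDW under hematology. An unscheduled blood sample on Day 250 lies in the hematology Month 9 window (Day 226 to 315) and also in the RDW Month 24 window. One tube of blood could therefore carry two visit labels.

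**5. What the windows do not feed.**

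- VOE-CR and sVOE-CR use Days 183 to 548 (SAP 4.4.1, 4.4.2.1).
- Globin Response refers to Table 12 only for scheduled globin visits, which are in a different block (SAP 4.4.2.2).
- CTCAE shift tables use the worst value within the time periods of SAP 3.11 (SAP 4.6.3).
- Karyotyping and NGS are summarised before Day 1, from Day 1 and overall (SAP 4.6.10).
- Urinalysis is only listed (SAP 4.6.3).

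**6. Weight of one substitution.** SAP Table 1 shows 36 subjects infused in Group C, so one substituted subject is 1/36 = 2.8% of a full Group C summary. The documents do not show whether any such subject exists.

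**The case against.** The best defence is that the rule is narrower than it looks. CRF visit labels come first. Table 12 applies only when the scheduled visit is missing and unscheduled or additional data exist, and the value nearest the target is then taken. A first window that opens at Day 1 also completes a partition of follow-up and is not an arithmetic slip. All of this stands, but it limits how often the problem can arise and does not remove it when the only value is early.

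Several stronger readings are tempting, and the documents do not support them:

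- **That many windows relabel early data as Month 12.** Every block opens at Day 1, but only one block does so into Month 12 and only RDW into Month 24. The others open into Month 1, 3 or 6.
- **That any RDW value, such as the last one before a Month 3 departure, becomes Month 24.** A value recorded at a scheduled Month 3 visit is not unscheduled. RDW is also not named in the protocol's hematology list or schedule. If it is collected only at Month 24, its window is harmless, though the SAP does not say so.
- **That a withdrawal visit always becomes Month 12.** The SAP does not say how an Early Termination visit is labelled on the CRF. If it is entered as Month 24, it is tabulated there by nominal visit and Table 12 is bypassed.
- **That the protocol's mandatory unscheduled PFT for lung complications feeds Month 12.** That test falls between Screening and conditioning, before Day 1 (protocol 6.2.25). A PFT during the transplant stay would be discretionary.
- **That laboratory safety shift tables are affected.** They use other time periods, as shown in the working.

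**Conclusion.** The point holds in limited form. As written, the SAP requires a lone early unscheduled or additional value to be tabulated as Month 12 for the annual tests, up to 359 days before target, or as Month 24 for RDW, up to 719 days before target. By-visit descriptive summaries and the PFT and MRI shift tables could be distorted; the documents do not show that they are.

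The conclusion assumes that the scheduled visit is missing, that no nearer value exists and, for withdrawals, that Early Termination data are not entered under a nominal Month 24 label. For RDW it also assumes that values are recorded before Month 24. The frequency of these conditions is unknown. The primary and key secondary analyses are untouched. This is a cheap improvement, and the trial's conclusions do not depend on it.

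**What to change.** Edit Table 12 and add one sentence to SAP 3.11.

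- **Annual tests:** start Month 12 at about Day 181 and keep the 540/541 cut. This mirrors the window's own late side: 360 − 180 = 180, with the window opening the day after.
- **RDW:** start Month 24 at Day 676, as for the other hematology tests.
- **Early Termination:** state that these data are assigned to windows by study day, whatever the CRF visit label.
- **Earlier values:** show them in listings only.

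Borrowing the half-yearly limits for the annual tests (Month 12 as Day 271 to 450, Month 24 from Day 631) would go too far. It would leave Days 451 to 630 unassigned, which is 630 − 451 + 1 = 180 days that the present table places sensibly. Changing the first Month 3 and Month 6 windows is optional and not needed here.

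The cost is a short edit and a few more missing Month 12 or Month 24 cells. For example, Early Termination tests at Day 100 would appear in listings and in no annual summary.

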6.3. Power and Success Criteria for VOE-CR, sVOE-CR and Globin Response

For the primary efficacy endpoint of VOE-CR, the power and success criterion in the table below are calculated based on the null hypothesis as 40% and alternative hypothesis as 80% at 1-sided alpha of 0.025 using Exact Test Per EAST® (Version 6). Likewise, for sVOE-CR, the null hypothesis is assumed to be 50% and alternative hypothesis be 85%. For Globin Response, the calculation is performed under the assumption of null hypothesis as 40% and alternative hypothesis as 70%.

Table 13. Power and Success Criteria for VOE-CR, sVOE-CR and Globin Response

Endpoint	Number of Subjects in the Analysis Population	Power [1]	Success Criteria: Number of Subjects Achieve the Endpoint
VOE-CR	35 (currently planned)	>99%	21
	34	>99%	20
	33	>99%	20
	32	>99%	19
	31	>99%	19
	30	>99%	18
	29	>99%	18
sVOE-CR	35 (currently planned)	>99%	24
	34	>99%	24
	33	>99%	23
	32	98%	23
	31	99%	22
	30	99%	21
	29	98%	21
Globin Response	41 (currently planned)	96%	24
	40	97%	23
	39	95%	23
	38	96%	22
	37	94%	22
	36	95%	21
	35	93%	21

[1] at 1-sided alpha of 0.025, using Exact Test Per EAST® (Version 6).

6.4. Definitions of VOE and sVOE

Table 14. Definitions of VOE and sVOE

	Definitions
Investigator VOE	
In the opinion of the investigator, the event meets any of the following VOE categories:
 
○ Acute pain with no medically determined cause other than VOE (e.g., VOC)○ Acute chest syndrome○ Acute hepatic sequestration○ Acute splenic sequestration○ Acute priapism 
These are all VOEs, irrespective of the severity, as reported by the investigator and can include VOEs managed at home.

Protocol VOE	
It is an investigator reported VOE and meets at least one criterion below:
 
1. The VOE category = "Acute pain with no medically determined cause other than VOE (e.g., VOC)" and Yes for all the sub-questions below:
- Duration > 2 hours?- Require care at a medical facility?2. The VOE category = "Acute chest syndrome" and Yes for all sub-questions below:
- Pneumonia-like symptoms (e.g., chest pain, fever [$>38.5^{\circ}\text{C}$], tachypnea, wheezing or cough, or finding upon lung auscultation)?- Presence of a new pulmonary infiltration consistent with ACS?- Requiring oxygen treatment and/or blood transfusion?3. The VOE category = "Acute hepatic sequestration" and Yes for all sub-questions below:
- Sudden enlargement of the liver with pain in the RUQ?- Abnormal results of LFTs not due to biliary disease?- Reduction in Hb concentration by at least 2 g/dL below the baseline value?4. The VOE category = "Acute splenic sequestration" and Yes for all the sub-questions below:
- Sudden enlargement of the spleen?- Reduction in Hb concentration by at least 2 g/dL below the baseline value?5. The VOE category = "Acute priapism" and Yes for all the sub-questions below:

Definitions	
	
 - Lasting more than 2 hours? - Require care at a medical facility?
Adjudicated VOE	It is a VOE as determined by adjudication committee after referring to protocol VOE definition and based upon the preponderance of the evidence, clinical knowledge, and expertise.
Protocol sVOE	
It is a protocol VOE and any of the following is Yes
 
  Hospitalization \geq 24 hours?  ER observation \geq 24 hours?  At least 2 visits to a day unit or ER over 72 hours with both visits requiring IV treatment?  Priapism lasting more than 2 hours requiring medical facility visit?
Adjudicated sVOE	It is a sVOE as determined by adjudication committee after referring to protocol sVOE definition and based upon the preponderance of the evidence, clinical knowledge, and expertise.

RUQ = right upper quadrant.

6.5. eGFR Formula

eGFR is reported as ml/min/SSA (x); Age is reported as years (x).

For purpose of reporting, 1.73m^2 has been given the unit of SSA, which is short for Standard Surface Area.

- For subjects \geq 18 years old, CKD-EPI creatinine equation for eGFR as below

Conventional: Serum creatinine is reported as mg/dL (x.xx) and the CKD-EPI equation ([Levey et al. 2009](#)) is below:

Race	Sex	Serum Creatinine (mg/dL)	Equation for eGFR by CKD-EPI
Black	Female	≤ 0.70	$166 \times (\text{Serum Creatinine}/0.7)^{-0.329} \times (0.993)^{\text{Age}}$
Black	Female	> 0.70	$166 \times (\text{Serum Creatinine}/0.7)^{-1.209} \times (0.993)^{\text{Age}}$
Black	Male	≤ 0.90	$163 \times (\text{Serum Creatinine}/0.9)^{-0.411} \times (0.993)^{\text{Age}}$
Black	Male	> 0.90	$163 \times (\text{Serum Creatinine}/0.9)^{-1.209} \times (0.993)^{\text{Age}}$
White or Other	Female	≤ 0.70	$144 \times (\text{Serum Creatinine}/0.7)^{-0.329} \times (0.993)^{\text{Age}}$
White or Other	Female	> 0.70	$144 \times (\text{Serum Creatinine}/0.7)^{-1.209} \times (0.993)^{\text{Age}}$
White or Other	Male	≤ 0.90	$141 \times (\text{Serum Creatinine}/0.9)^{-0.411} \times (0.993)^{\text{Age}}$
White or Other	Male	> 0.90	$141 \times (\text{Serum Creatinine}/0.9)^{-1.209} \times (0.993)^{\text{Age}}$

SI: Serum creatinine is reported as umol/L (x.xx), and the CKD-EPI equation is below:

Race	Sex	Serum Creatinine (umol/L)	Equation for eGFR by CKD-EPI
Black	Female	≤ 61.9	$166 \times (\text{Serum Creatinine} \times 0.011312/0.7)^{0.329} \times (0.993)^{\text{Age}}$
Black	Female	> 61.9	$166 \times (\text{Serum Creatinine} \times 0.011312/0.7)^{-1.209} \times (0.993)^{\text{Age}}$
Black	Male	≤ 79.6	$163 \times (\text{Serum Creatinine} \times 0.011312/0.9)^{-0.411} \times (0.993)^{\text{Age}}$
Black	Male	> 79.6	$163 \times (\text{Serum Creatinine} \times 0.011312/0.9)^{-1.209} \times (0.993)^{\text{Age}}$
White or Other	Female	≤ 61.9	$144 \times (\text{Serum Creatinine} \times 0.011312/0.7)^{0.329} \times (0.993)^{\text{Age}}$
White or Other	Female	> 61.9	$144 \times (\text{Serum Creatinine} \times 0.011312/0.7)^{-1.209} \times (0.993)^{\text{Age}}$
White or Other	Male	≤ 79.6	$141 \times (\text{Serum Creatinine} \times 0.011312/0.9)^{-0.411} \times (0.993)^{\text{Age}}$
White or Other	Male	> 79.6	$141 \times (\text{Serum Creatinine} \times 0.011312/0.9)^{-1.209} \times (0.993)^{\text{Age}}$

Note: Conversion factor for serum creatinine umol/L $\times 0.011312 = \text{mg/dL}$

- For subjects < 18 years old, Bedside-Schwartz equation for eGFR ([Schwartz et al 2019; Schwartz and Work 2019](#)) as below

Conventional:

eGFR by Schwartz = $0.413 \times (\text{Height}/\text{Enzymatic serum creatinine})$, where:

- Enzymatic serum creatinine is reported in mg/dL (x.xx)
- Height is reported in cm (x.x)

SI:

eGFR by Schwartz = $0.413 \times (\text{Height}/\text{Enzymatic serum creatinine} \times 0.011312)$, where:

- Enzymatic serum creatinine is reported in umol/L (x.xx)
- Height is reported in cm (x.x)

6.6. Statistical Methods for Confidence Interval of Percentage of Reduction in Annualized sVOE or VOE

This section presents the 1-sided of 97.5% CI for percentage reduction in annualized sVOE in the 24 months after drug product infusion from baseline. The same statistical methods will be used for the corresponding annualized number of VOE analysis.

sVOE is count outcome. Hence, it is reasonable to assume the targeted patient sub-population has an underlying distribution Poisson (λ).

Assuming the sVOE data consist of $(N_{i0}, N_{i1}, T_{i0}, T_{i1})$, $i = 1, \dots, k$, where N_{i0} and T_{i0} are the number of sVOEs and follow-up time prior to Informed Consent, serving as baseline data, respectively, and N_{i1} and T_{i1} are the number of sVOEs and follow-up time after the treatment, respectively. In Study HGB-206, $T_{i0} = 2$ years for every subject.

We assume that given λ_{i0} and λ_{i1} , $N_{i0} \sim \text{Poisson}(\lambda_{i0}T_{i0})$, and $N_{i1} \sim \text{Poisson}(\lambda_{i1}T_{i1})$ are two conditionally independent variables with a common ratio

$$r = \frac{\lambda_{i1}}{\lambda_{i0}}, i = 1, \dots, k,$$

where r is the parameter of interest. Also note that sVOE reduction can be noted as θ , where $\theta = (1 - r)$.

Under this model, according to (Krishnamoorthy and Thomson 2004),

$$N_{i1}|N_i \sim \text{Binomial}\left(N_i, \frac{rT_{i1}}{T_{i0} + rT_{i1}}\right),$$

where $N_i = N_{i0} + N_{i1}$.

The following test statistics can be used to construct a 1-sided confidence interval (CI) for r :

$$T = \sum_{i=1}^k N_{i1}.$$

For any given value $r_0 > 0$, one can assume the observed test statistics is t . Thus, the p-value can be calculated as

$$p(r_0) = P(T \leq t|r = r_0).$$

Clearly, $p(r)$ can be calculated easily with Monte Carlos method: we only need to simulate

$$T^* \sim \sum_{i=1}^k \text{Binom}\left(N_i, \frac{rT_{i1}}{T_{i0} + rT_{i1}}\right)$$

by a large number of times and calculate

$$p(r) = B^{-1} \sum_b^B I(T_b^* \leq t).$$

In the end, a 1-sided 97.5% confidence interval for r can be constructed as $\{r: p(r) \geq 0.025\}$.

Note that our model has very general assumptions although we assume N_{i0} and N_{i1} follow a conditional Poisson distribution. This assumption is quite general because the baseline incidence rate, λ_{i0} , can vary from patient to patient and does not have any distribution requirement. As a special case, assuming λ_{i0} and λ_{i1} follow a gamma distribution across all patients, then N_{i0} and N_{i1} follow a negative binomial distribution. This means that our model is still valid even if there is a big variation in baseline sVOE.

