4.4.3.4. SCD Burden and Chronic Complications Assessments

These SCD burden and chronic complications assessments will be presented in table summaries by group for all subjects in TP. All data will be presented in listings.

The absolute change at each visit from baseline will be summarized by group.

- **Change from baseline in renal function as measured by eGFR**
eGFR will be calculated by CKD-EPI formula for subjects ≥ 18 years old and Schwartz formula for subjects < 18 years old. The formulas can be found in [Appendix 6.5](#).
- **Change from baseline in cardiac-pulmonary function via TRJV, PFTs and LVEF**
 - TRJV over time for each subject will be classified into 2 categories: < 2.5 m/s versus ≥ 2.5 m/s. A shift table will be presented to show the change from baseline in TRJV classification. The change from baseline values in TRJV will be presented in a listing.
 - Pulmonary Function Tests (PFTs) over time of each subject will be classified into one of the five categories indicated in [Table 5](#). A shift table will be presented to show the change from baseline in PFTs classification.

Table 5. Classification of Pulmonary Function

Category of Pulmonary Function	% of Predicted value					FEV1/ FVC
	FEV1	FVC	TLC ^[1]	RV	DLco	
Normal	$\geq 80\%$	$\geq 80\%$	$\geq 80\%$	$\geq 80\%$	$\geq 80\%$	$\geq 70\%$
Obstructive	$< 80\%$	$< 80\%$	$\geq 80\%$	$\geq 80\%$	$\geq 80\%$	$< 70\%$
Restrictive: meet any situation below						

Category of Pulmonary Function	% of Predicted value					FEV1/ FVC
	FEV1	FVC	TLC ^[1]	RV	DLco	
situation 1	<80%	<80%	<80%		<80%	≥70%
situation 2	≥ 80%	≥ 80%	<80%	<80%	≥ 80%	≥70%
situation 3			<80%		<80%	
Mixed obstructive and restrictive			<80%	<80%	≥ 80%	<70%
Isolated low DLco	≥ 80%	≥ 80%	≥ 80%	≥ 80%	<80%	≥70%

DLco = carbon monoxide diffusing capacity; FEV1 = forced expiratory volume in 1 second; FVC = forced vital capacity; RV = respiratory volume; TLC = total lung capacity.

^[1] % predicted FEV1, FVC, RV and DLco are directly collected in the CRF. Predicted values for TLC are derived using the formulas below, and height (meter) is subject's height at the time of the assessment or at the closest time to the assessment.

Male (age 4 – 17 years): $10.0^{**}(-2.0018 + 2.5698 \cdot \log_{10}(\text{HEIGHT} \cdot 100)) / 1000$.

Male (age ≥18 years): $0.066^*(\text{HEIGHT} \cdot 100) - 5.79$

Female (age 4 – 17 years): $10.0^{**}(-2.033 + 2.5755 \cdot \log_{10}(\text{HEIGHT} \cdot 100)) / 1000$

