4.6.3. Laboratory Data

Clinical laboratory values will be expressed using the International System of Units (SI), except g/dL and 10⁹/L will be used for hemoglobin and nucleated erythrocytes, respectively. Values will be summarized for each clinical laboratory parameter, including hematology, clinical chemistries, and iron studies, as specified below, and in the schedule of events.

The laboratories' own reference ranges are used as the default. In the absence of these ranges, refer to the Global Reference Range (GRR) Sources identified in [Table 6](#). Age- and sex-specific ranges will be used to flag out of range values and to indicate CTCAE (version 4.03) grade, where applicable.

The versions of the GRRs being utilized for this study are footnoted below. If revised GRRs are published during the study, the version will not automatically update.

Table 6. Global Reference Range Sources

Source	Version	Purpose
Kratz A, et al. "Laboratory Reference Values". N Engl J Med. 2004;351: 1548-63.	N Engl J Med. 2004;351: 1548-63	Adult Ranges
Mayo Clinic	Updated regularly online ^[1]	Children Ranges
Brown A. NHS Blood Sciences Department of Immunology and Immunogenetics. "Immunology Age Related Reference Ranges". QPR No. IMMQ0066.	Version No. 1.4	Immunology Age-Related Reference Ranges
Shearer W, et al. "Lymphocyte subsets in health children from birth through 18 years of age: The Pediatric AIDS Clinical Trials Group P1009 study." J Allergy Clin Immunol. 2003; 112: 973-80.	J Allergy Clin Immunol. 2003; 112: 973-80.	Lymphocyte Subsets in Pediatrics ages 0 to 18

^[1]<https://www.mayocliniclabs.com/test-info/pediatric/refvalues/index.html>

Descriptive statistics on the laboratory parameters listed in [Table 7](#) below, but may not be limited to, will be presented by visit, and where applicable, change from baseline will also be provided.

Table 7. List of Laboratory Parameters

Hematology	Iron Contents

 • Complete blood count (CBC) with differential • Haptoglobin • Nucleated erythrocytes • Platelet count • Reticulocyte count • Methemoglobin • Red cell distribution width (RDW) 	
 • Iron saturation (transferrin saturation) • Serum ferritin • Serum transferrin receptor • Serum transferrin • Liver iron content • Cardiac iron content (if assessed at baseline)
Serum Chemistry and Liver Function	

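### The SI CKD-EPI rows for women with creatinine at or below 61.9 µmol/L show exponent +0.329 instead of −0.329, which can reverse or mask eGFR change from baseline

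*SAP*

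**What the plan says.** SAP 4.4.3.4 defines the renal endpoint. It states that "eGFR will be calculated by CKD-EPI formula for subjects" aged 18 or over, uses a Schwartz formula below 18, and points to the appendix for the equations. For this group of endpoints, "The absolute change at each visit from baseline will be summarized by group".

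SAP 6.5 presents the CKD-EPI equation in two tables of eight rows. One is introduced by "Conventional: Serum creatinine is reported as mg/dL (x.xx) and the CKD-EPI equation" and the other by "SI: Serum creatinine is reported as umol/L (x.xx), and the CKD-EPI equation is below". The section gives a conversion factor of 0.011312 from µmol/L to mg/dL. It does not say which table the program uses.

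For women in the lower creatinine range:

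- Black, conventional (at or below 0.70 mg/dL): "166 \times (\text{Serum Creatinine}/0.7)^{-0.329"
- Black, SI (at or below 61.9 µmol/L): "166 \times (\text{Serum Creatinine} \times 0.011312/0.7)^{0.329"
- White or Other, conventional: coefficient 144, exponent −0.329
- White or Other, SI: "144 \times (\text{Serum Creatinine} \times 0.011312/0.7)^{0.329"

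SAP 4.6.3 adds that "Clinical laboratory values will be expressed using the International System of Units (SI"), with exceptions only for hemoglobin and nucleated erythrocytes. Table 9 in that section holds creatinine in µmol/L.

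**The concern.** The two tables are meant to be the same equation in different units, yet they disagree in the sign of one exponent for the same women. With a positive exponent, eGFR rises as creatinine rises to 61.9 µmol/L and then falls under the −1.209 row, so two different creatinine values can give the same eGFR.

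Change in eGFR from baseline is a named secondary endpoint. If the SI rows were programmed as shown, a real rise in creatinine in these women could be summarised as a gain in renal function or as almost no change. The distorted values still look plausible, so routine range checks may not reveal the fault.

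**Working it through.** **Inputs.** Coefficients, cut-points, exponents and the conversion factor are from SAP 6.5. The eligibility floor of 70 mL/min/1.73 m² is from Protocol 4.3, exclusion 12. The ages and creatinine values are assumptions for illustration.

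**Step 1: do the tables otherwise agree?** The cut-points convert correctly: 0.7/0.011312 = 61.88 (SAP: 61.9) and 0.9/0.011312 = 79.56 (SAP: 79.6). Six of the eight SI rows match their conventional rows in coefficient, divisor and exponent. The other two, both for women at or below 61.9 µmol/L, differ only in the sign of the exponent. Of the 16 creatinine exponents in the two tables, 14 carry a minus sign.

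**Step 2: formulas compared.** With c = 166 (Black) or 144 (White or Other):

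- Conventional: c × (Scr/0.7)^(−0.329 if Scr ≤ 0.70, otherwise −1.209) × 0.993^age
- SI as shown: c × (µmol/L × 0.011312/0.7)^(+0.329 if µmol/L ≤ 61.9, otherwise −1.209) × 0.993^age

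**Step 3: error in a single value.** The ratio of the value as shown to the conventional value is (µmol/L × 0.011312/0.7)^0.658:

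| Creatinine, µmol/L | 30 | 40 | 50 | 60 | 61.9 |
|---|---|---|---|---|---|
| Ratio | 0.62 | 0.75 | 0.87 | 0.98 | 1.00 |

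**Step 4: error in the change from baseline.** Age 25 at baseline and 27 at follow-up, so the age factors are 0.993^25 = 0.8389 and 0.993^27 = 0.8272. Worked example for a Black woman going from 0.45 to 0.65 mg/dL (39.8 to 57.5 µmol/L):

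- Conventional: 166 × (0.45/0.7)^−0.329 × 0.8389 = 161.1; 166 × (0.65/0.7)^−0.329 × 0.8272 = 140.7; change −20.3.
- SI as shown: 166 × (0.45/0.7)^0.329 × 0.8389 = 120.4; 166 × (0.65/0.7)^0.329 × 0.8272 = 134.0; change +13.6.

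All changes below are taken before rounding.

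| Creatinine, mg/dL | Black: conventional | Black: SI as shown | White or Other: conventional | White or Other: SI as shown |
|---|---|---|---|---|
| 0.45 to 0.65 | −20.3 | +13.6 | −17.6 | +11.8 |
| 0.55 to 0.65 | −10.1 | +5.4 | −8.7 | +4.7 |
| 0.60 to 0.65 | −5.8 | +1.6 | −5.0 | +1.4 |
| 0.45 to 0.80 | −44.2 | −3.6 | −38.3 | −3.1 |

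In the last line the follow-up value falls in a correct row; the error comes entirely from baseline. At a fixed age the sign is always reversed when both values are at or below 61.9 µmol/L. When only one is, the change can be reversed, masked or attenuated.

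**Step 5: same eGFR from different creatinine.** For a Black woman aged 25 at 0.50 mg/dL (44.2 µmol/L), the higher creatinine giving the same eGFR is 0.7 × (0.7/0.5)^(0.329/1.209) = 0.767 mg/dL (67.8 µmol/L). The SI rows as shown give 124.7 for both. The conventional rows give 155.6 and 124.7.

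**Step 6: would the error be visible?** The lowest eGFR from the two rows as shown, over 30 to 61 µmol/L and ages 18 to 50, is 79.9 (coefficient 144, age 50, 30 µmol/L). That is above the eligibility floor of 70, so over this range the effect is on change summaries and not on that threshold.

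**The case against.** The strongest objection is that the SAP text was read from a PDF by a program, and the whole point rests on one superscript character. Other superscript markers are rendered inconsistently elsewhere in the text, so a lost minus sign is possible. This stands as a reason to look at the original page first. Against it, 14 of 16 minus signs survived, and the two missing ones are exactly the matching pair of female SI rows. That pattern fits one row having been copied from the other better than it fits random loss.

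Second, harm needs two further conditions: that the SI table is the one programmed, and that the program copied the sign. The SAP establishes neither. The SI-units statement sits in the safety section and does not say which table feeds the efficacy endpoint. The tests are run at local laboratories, and Protocol 6.2.7 lists eGFR itself among the laboratory parameters. If creatinine is used in or converted to mg/dL, nothing changes. These conditions stand. Still, SAP 4.4.3.4 says eGFR will be calculated, and creatinine held in µmol/L makes use of the SI table plausible.

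Third, the conventional rows make the intended equation clear, and the endpoint is descriptive. Both are true. They limit the severity and make the correction easy, but they do not make the SI rows right.

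Finally, creatinine rises of 44% and 78% are large. With 0.60 to 0.65 mg/dL the discrepancy is smaller, but the sign still reverses.

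**Conclusion.** The concern holds. As the text stands, two SI rows contradict their conventional counterparts, and nothing in the SAP can explain a change of sign. If they were programmed as shown, the eGFR change in the affected women would be wrong in direction or size: from −20.3 to +13.6 or from −44.2 to −3.6 in the illustrations for a Black woman, and from −5.8 to +1.6 for a small rise.

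The conclusion is conditional on the original page and on the program. It concerns only women aged 18 or over with creatinine at or below 61.9 µmol/L at baseline or follow-up; the documents do not say how many there are. Men, subjects under 18 and values above 61.9 µmol/L use other rows. eGFR also enters the laboratory summaries and CTCAE shift tables, but no change of grade is claimed. VOE-CR, sVOE-CR and Globin Response are untouched. This should be fixed; confidence is medium because of the PDF reading and the unstated unit form.

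**What to change.** 1. Check the exponent on the original page of SAP 6.5. If the minus sign is absent, change both SI rows for women at or below 61.9 µmol/L to −0.329.
2. State in 6.5 which unit form is programmed.
3. Test the eGFR program against the conventional rows, using values on both sides of 61.9 µmol/L. Re-run the eGFR change-from-baseline and other eGFR outputs only if the program used +0.329.
4. While editing the section, put brackets around creatinine × 0.011312 in the SI Schwartz formula, so that height is divided by the converted value. This is notation only.

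The cost is one page check, a correction of two appendix rows, one added sentence and a program check. No new data are needed.
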